#### **3.2. Protocol Violations**

At the discretion of the sponsor, major protocol violations as determined by a review of the data prior to unblinding of the study results and the conduct of statistical analyses may result in the removal of a subject's data from the Per Protocol Population. The sponsor, or designee, will be responsible for producing the final protocol violation file (formatted as a Microsoft Excel file), in collaboration with Cytel and the data monitoring group as applicable; this file will include a description of the protocol violation, and clearly identify whether or not this violation warrants exclusion from the Per Protocol Population. This file will be finalized prior to hard database lock.

All protocol violations will be presented in the data listings.

## 4. STATISTICAL METHODS

### 4.1. Sample Size Justification

Approximately 240 male and non-gravid female subjects aged 18-80 with moderate to severe active UC will be randomized.

Prior studies suggest treatment effects of ~21 percentage point differences from placebo clinical remission rate of ~10%. Those values were assumed for purposes of design of this 12-week treatment trial.

Table 2 below shows power for representative scenarios of potential TRUE underlying dose-response relationships, as well as that for no drug effect to assess type 1 error (calculations via Cytel's EAST COMPASS adaptive dose-finding software based on 1000 simulations of each design, with each simulated trial analyzed as described in Section 4.6).

**Table 2 Power and Type 1 Error for Various Response Rates**

TRUE underlying response rates				power (alpha=0.025, 1-sided)			
placebo	150 mg	300 mg	900 mg	N=260	N=240	N=220	N=200
0.1	0.2	0.31	0.31	93%	91%	90%	84%
0.1	0.17	0.24	0.31	83%	82%	78%	75%
0.1	0.1	0.1	0.1	3.4%	2.2%	1.7%	2.1%

### 4.2. General Statistical Methods and Data Handling

#### 4.2.1. General Methods

All output will be incorporated into Microsoft Excel or Word files, sorted and labeled according to The International Council for Harmonisation of Technical Requirements for Pharmaceuticals for Human Use (ICH) recommendations, and formatted to the appropriate page size(s).

Tabulations will be produced for appropriate demographic, baseline, efficacy, pharmacokinetic, pharmacodynamic and safety parameters. For categorical variables, summary tabulations of the number and percentage within each category (with a category for missing data) of the parameter will be presented. For continuous variables, the mean, median, standard deviation, minimum and maximum values will be presented.

Formal statistical hypothesis testing will be performed on the primary efficacy endpoint with all tests conducted at the 1-sided, 0.025 level of significance. Summary statistics will be presented, as well as confidence intervals on selected parameters, as described in the sections below.

#### 4.2.2. Computing Environment

All descriptive statistical analyses will be performed using SAS statistical software (Version 9.2), unless otherwise noted. Medical History and adverse events will be coding using the most current MedDRA version available. Concomitant medications will be coded using the most current World Health Organization (WHO) Drug version available and WHODRUG DD B Format.

#### 4.2.3. Methods of Pooling Data

Data will be pooled across all study sites for analyses. Homogeneity of the treatment effect across sites will be evaluated using a logistic regression model with response rate as the dependent variable and terms for treatment, site, and treatment by site interaction as fixed effects. Sites with small enrollment numbers will be pooled with the closest geographical site, as necessary, to ensure model convergence.

#### 4.2.4. Adjustments for Covariates

The analyses may be adjusted for the randomization stratification factor, prior treatment with TNF- $\alpha$  antagonist. It will be used in the stratified primary efficacy analysis, and as a covariate in models used for continuous endpoints.

#### 4.2.5. Multiple Comparisons/Multiplicity

Multiplicity will be addressed via a closed testing procedure with combined p-values computed for each of the two stages of the trial (interim analysis and post-interim analysis). Each stage p-value will be adjusted as appropriate by a closed testing multiple comparison approach that controls the overall type 1 error at alpha equal to 0.025, one-sided. Further details will be provided in Section 4.6.

Testing of secondary endpoints will only be performed if the primary efficacy null hypothesis is rejected. A hierarchical testing procedure will be used for the multiple secondary endpoints at the 0.025 (one-sided) alpha level. The first ten secondary endpoints will be tested in the order that they are presented in Section 2.5.1. For secondary endpoints compared at multiple time points, only the comparison at Week 12 will be used for hierarchical testing purposes.

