## 2.5. Efficacy, Pharmacokinetic, and Safety Variables

### 2.5.1. Efficacy Variables

The primary efficacy endpoint for this study is the proportion of subjects receiving PTG-100 with clinical remission at Week 12 compared with placebo.

Clinical remission is defined as follows using the Mayo subscores of stool frequency, rectal bleeding, and endoscopy:

1. Stool frequency subscore of 0 or 1 with a pre-specified change of 1 or more from baseline
2. Rectal bleeding subscore of 0
3. Endoscopy subscore of 0 or 1 (modified so that a score of 1 does not include friability)

Secondary endpoints, all based on comparison of individual PTG-100 dose levels with placebo, include:

1. Proportion of subjects with clinical response at Week 12 (Day 84) (defined as at least 1 point and 30% reduction from baseline in rectal bleeding and stool frequency subscores)
2. Proportion of subjects with endoscopic response at Week 12 (Day 84) (defined as an endoscopic subscore of 0 or 1)
3. Mean change in endoscopy subscore from baseline to Week 12 (Day 84)
4. Mean change in rectal bleeding subscore from baseline to Weeks 2, 4, 6, 8, 10, 12, and 16 (Days 14, 28, 42, 56, 70, 84, and 112)
5. Mean change in stool frequency subscore from baseline to Weeks 2, 4, 6, 8, 10, 12, and 16 (Days 14, 28, 42, 56, 70, 84, and 112)
6. Proportion of subjects with endoscopic remission at Week 12 (defined as an endoscopic subscore of 0)
7. Mean change in Complete Mayo Score (including all four subscores) from baseline to Week 12 (Day 84)
8. Mean change in Partial Mayo Score (excluding endoscopy subscore) from baseline to Weeks 2, 4, 6, 8, 10, 12, and 16 (Days 14, 28, 42, 56, 70, 84, and 112)
9. Mean change in fecal calprotectin levels from baseline to Weeks 6 (Day 42) and 12 (Day 84)
10. Mean change in IBDQ score from baseline to Week 12 (Day 84)

Exploratory endpoints include:

1. Mean change in histological score from baseline to Week 12
2. Effects of ADA on PK, safety, and efficacy in subjects with positive ADA

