#### **4.6. Efficacy Evaluations**

##### **4.6.1. Primary Efficacy Analysis**

The primary efficacy endpoint for this study is the proportion of subjects receiving PTG-100 with clinical remission at Week 12 compared with placebo, as defined in Section 2.5.1.

Efficacy analysis for the primary endpoint will be conducted using the FAS population and will be repeated on the PP population as a sensitivity analysis.

The proportion of subjects with clinical remission at Week 12 will be calculated and reported with a two-sided 95% exact confidence interval as an estimate of the true proportion of subjects with clinical remission in the target patient population. Two approaches will be used to report the percentages:

Approach 1: The naïve percentage and associated 95% CI for each dose group, based on data combined across both stages of the trial.

Approach 2: For doses that are selected for Stage 2, the Stage 2-only proportion of subjects with clinical remission and 95% CI will be reported. For doses not selected for Stage 2, the proportions and associated 95% CI based on Stage 1 data only will be reported.

Analysis to examine treatment effect (i.e. odds ratio for clinical remission among subjects with each active dose vs. placebo and 95% CI) will be carried out at the Week 12 time point, employing a Cochran-Mantel-Haenszel test stratified for prior TNF- $\alpha$  use (yes/no). Raw p-values, unadjusted for multiple comparisons, associated with each odds ratio will also be presented.

To obtain the primary endpoint study p-values, Simes-adjusted p-values for each dose regimen vs. placebo that are produced for the primary endpoint from the first and second stages of the study will be combined by using the inverse normal combination function to obtain the final p-value.

The components contributing to the Stage 1 portion of the p-value will include data of subjects from all 4 original dose groups (placebo, low, medium, high dose) who were enrolled during Stage 1, defined as on or before the data snapshot date for the interim look at efficacy.

The components contributing to the Stage 2 portion of the p-value will be data from subjects from the dose groups that were not discontinued who were enrolled after the date of the data snapshot for the interim look at efficacy.

The final p-value for the trial primary endpoint will be a weighted combination of the two components, as described below.

The null hypothesis to be tested is

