$$H_0: \pi_C = \pi_L = \pi_M = \pi_H$$

against the alternative hypothesis

$$H_1: \text{at least one of } \pi_L, \pi_M, \pi_H \text{ is different from } \pi_C$$

where  $\pi_C$  is the response rate for placebo arm, and  $\pi_L, \pi_M, \pi_H$  are the response rates for the three active dose groups. Let  $w_1 = \sqrt{t_1}$  and  $w_2 = \sqrt{1 - t_1}$  be the prespecified weights where  $t_1$  is the statistical information time for interim analysis. Let  $p_{1L}, p_{1M}, p_{1H}$  be the marginal p-values for the three comparisons based on the test statistics of difference of proportions between active dose and placebo group. The test is left tailed. Let  $p_{1(1)} \leq p_{1(2)} \leq p_{1(3)}$  be the ordered p-values. Let  $\tilde{p}_1$  be the Simes adjusted p-value based on the first stage data. Then

$$\tilde{p}_1 = \min\{3p_{1(1)}, \frac{3}{2}p_{1(2)}, p_{1(3)}\}.$$

Let  $p_2$  be the p-value for the comparison for the selected dose versus placebo group. The final combined Simes p-value is given by

$$\Phi(w_1\Phi^{-1}(\tilde{p}_1) + w_2\Phi^{-1}(p_2))$$

where  $\Phi(\cdot)$  is the cumulative distribution function of standard normal variable and  $\Phi^{-1}(\cdot)$  is the inverse cumulative distribution function of standard normal variable.

The final analysis is significant if

$$\Phi(w_1\Phi^{-1}(\tilde{p}_1) + w_2\Phi^{-1}(p_2)) \leq \alpha$$

which is the same as

$$p_2 \leq \Phi \left\{ \frac{\Phi^{-1}(\alpha) - w_1 \Phi^{-1}(\tilde{p}_1)}{w_2} \right\}$$

Analyses of the primary endpoint will be conducted separately for the subjects with prior TNF-alpha use and those without prior TNF-alpha use. Treatment effect estimates will be reported using the naïve odds ratio estimator and its associated 95% CI. P-values will be derived from unstratified Cochran-Mantel-Haenszel tests.

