#### 4.6.2. Secondary Efficacy Analyses

Analyses for the secondary endpoints will be conducted using the FAS and PP populations. Where applicable, baseline is defined as the last non-missing pre-treatment assessment prior to initiation of study treatment.

All secondary endpoints that reflect a dichotomous response will be analyzed in the same manner as the primary efficacy endpoint. These secondary endpoints include

- Proportion of subjects with endoscopic response at Week 12 (Day 84) (defined as an endoscopic subscore of 0 or 1)
- Proportion of subjects with clinical response at Week 12 (Day 84) (defined as at least 1 point and 30% reduction from baseline in rectal bleeding and stool frequency subscores)
- Proportion of subjects developing neutralizing antidrug antibodies (ADA)
  - Methods for detection of ADA in clinical samples are presented in Section 7.8 of the protocol
- Proportion of subjects with endoscopic remission at Week 12 (defined as an endoscopic subscore of 0)

Hypothesis testing for all continuous secondary endpoints will be conducted using repeated measures mixed analysis of covariance model adjusted for treatment, time point, treatment-by-time point interaction, stratification factor (TNF-alpha prior use) and baseline values. For subjects who withdraw prematurely, the last observation will be carried forward. These analyses will be based on the Stage 1 and Stage 2 combined data for exploratory purposes. Pairwise comparisons of active drug versus placebo for the change from baseline endpoints will be conducted and p-values derived as described in the analysis of the primary efficacy endpoint. In addition, a summary of observed values and change from baseline values will be presented for each endpoint. Graphical summaries by treatment group of mean change from baseline over time up to Week 12 will also be presented.

Continuous secondary endpoints include

- Mean change in complete Mayo Score (including all four subscores) from baseline to Week 12
- Mean change in Partial Mayo Score (excluding endoscopy subscore) from baseline to Weeks 2, 4, 6, 8, 10, 12, and 16 (Days 14, 28, 42, 56, 70, 84, and 112)
- Mean change in endoscopy subscore from baseline to Week 12 (Day 84)
- Mean change in rectal bleeding and stool frequency subscores from baseline to Weeks 2, 4, 6, 8, 10, 12, and 16 (Days 14, 28, 42, 56, 70, 84, and 112)
- Mean change in fecal calprotectin levels from baseline to Weeks 6 and 12

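### Entry to the secondary hierarchy rests on one null for all doses, and the SAP does not say how individual doses move through the chain

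*SAP*

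**What the plan says.** **Entry condition.** SAP 4.2.5: "Testing of secondary endpoints will only be performed if the primary efficacy null hypothesis is rejected". The null is in the singular.

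**Which null.** SAP 4.6.1 displays one only. It is introduced by "The null hypothesis to be tested is" and reads "H_0: \pi_C = \pi_L = \pi_M = \pi_H". The alternative is that at least one dose differs from placebo.

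**The chain.** SAP 4.2.5: "A hierarchical testing procedure will be used for the multiple secondary endpoints at the 0.025 (one-sided) alpha level", and "The first ten secondary endpoints will be tested in the order that they are presented in Section 2.5.1". SAP 2.5.1 lists exactly ten. Where an endpoint has several time points, only Week 12 counts.

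**What each step tests.** SAP 2.5.1: "Secondary endpoints, all based on comparison of individual PTG-100 dose levels with placebo, include".

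**How doses are handled within an endpoint.** SAP 4.6.2 analyses the binary secondaries like the primary. For the continuous ones it asks for pairwise comparisons with "p-values derived as described in the analysis of the primary efficacy endpoint".

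**Status.** SAP 4.6.2 also says of the continuous secondaries: "These analyses will be based on the Stage 1 and Stage 2 combined data for exploratory purposes". SAP 4.2.1 mentions formal hypothesis testing for the primary endpoint only.

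**What is not said.** No section makes a dose's secondary tests depend on that dose's own remission result. None says whether there is one chain or one per dose, or what happens when one dose passes a step and the other fails. Protocol 7.4 contains no secondary hierarchy, so it does not fill the gap.

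**The concern.** The null that opens the hierarchy is about the doses jointly, while the claims that follow are about doses singly. One effective dose is enough to reject the joint null. Nothing in the text then stops a second dose that failed on remission from being formally tested on clinical response, endoscopic response and the rest.

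The closed test within each endpoint does not remove the problem. It protects against picking the best dose on a given endpoint. An effective dose tends to reject the intersection hypothesis at every step, which leaves the other dose tested at close to the full 0.025 each time. How far error then builds up depends on the progression rule, and the SAP does not give one.

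At stake is secondary objective 1 (Protocol 3): dose-response and the choice of induction regimens. A formally significant secondary result for a dose that failed on remission could weigh in that choice. An unstated progression rule could also be settled after unblinding.

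**Working it through.** **1. The plan's own figures.** SAP Table 2 gives 91%, 82% and 2.2% at N=240 for the two effect scenarios and the null. I simulated two stages with Stage 1 N=60, two doses kept, Simes within stage, inverse normal combination and a full closed test.
- Pooled variance, no overrun: 91.1%, 81.7%, 1.8%.
- Unpooled variance, overrun of 60: 90.0%, 81.3%, 2.1%.

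These agree within simulation error. With 1000 runs the standard error at 2.2% is √(0.022×0.978/1000), about 0.5 points. The primary test, read as a closed test, is not the difficulty here. No scenario in Table 2 pairs an inert dose with an effective one.

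**2. Inputs.**
- From the documents: one-sided 0.025; ten steps; one or two doses continuing (SAP 2.2); remission 10% against 31% (SAP 4.1); 70–80 per selected arm, 70 used (SAP 2.1).
- Derived: the mean of the remission z-statistic is 0.21/√(2×0.205×0.795/70) = 0.21/0.0682 = 3.08, so power is Φ(3.08 − 1.96) = 87%.
- Assumed: dose A works on every endpoint and dose B on none; the arms are equal with a shared placebo (correlation 0.5 between doses); the correlation between endpoints and the power per secondary step vary over ranges.

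**3. Hand check, common chain that moves on when any dose passes, independent endpoints.** Step k is open with probability of about π^k, where π is dose A's power per step. Expected open steps = π(1 − π^10)/(1 − π), and each exposes dose B to 0.025.
- π = 0.70: 2.27 × 0.025 = 5.7%
- π = 0.87: 5.03 × 0.025 = 12.6%
- π = 0.95: 7.62 × 0.025 = 19.1%

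These are expected numbers of false claims, so the chance of at least one is lower. If the chain never stops, that chance is 1 − 0.975^10 = 22.4%.

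**4. Simulation with correlated endpoints.** Chance that inert dose B gains at least one false secondary claim:

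| Reading of SAP 4.2.5 | All trials | Trials in which B also failed remission |
|---|---|---|
| Common chain, moves on if any dose passes; single analysis, correlation 0–0.9 | 6–18% | 4–17% |
| Same, two-stage closed test (20 + 50 per arm) | 4–12% | 3–11% |
| Common chain, correlation 0.3–0.7, power 70–95% at every step; single analysis | 6–15% | 5–13% |
| Same, two-stage closed test | 5–13% | 4–12% |
| Chain stops unless both doses pass | 2.0–2.5% | – |
| Joint entry condition, then one chain per dose | 2.0–2.5% | – |
| Entry condition and chain both per dose | 0.0–1.5% | none possible |

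Rows 1–2 take remission power from the design rates (the hierarchy opens in about 69% of two-stage trials). Rows 3–4 set 70–95% power at every step, remission included.

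**5. Cost of the readings that control error.**
- *All doses must pass.* With one inert dose, the effective dose gets beyond the first secondary in only about 2–2.5% of trials.
- *One chain per dose at 0.025.* Each dose is held to 2.5%. Over two doses the bound is 2 × 2.5% = 5%. If both are null on the first secondary and each is tested there at the full 0.025, the rate is 0.05 − 0.0046 = about 4.5% at correlation 0.5, where 0.0046 is the chance that both are rejected. Keeping a Simes adjustment across doses at that endpoint lowers this case to 2.5%, but the SAP does not say how such an adjustment works once the chains are at different steps.

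**The case against.** The strongest reply is that the SAP nowhere prescribes a common chain. It specifies closed testing, and SAP 4.6.1 produces Simes-adjusted p-values for each regimen against placebo, so a dose-by-dose reading of the entry condition is open. Two readings keep an inert dose at 2.5% or less, and one of them keeps the joint entry condition, so that condition alone does not inflate error.

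The scenario is also narrow. Two doses must continue, one effective nearly everywhere and one inert everywhere, although the interim analysis exists partly to drop ineffective arms. If the seven continuous secondaries are exploratory, three binary endpoints remain, and even the sum bound is 3 × 2.5% = 7.5%. Finally, this is Phase 2b and the primary claim is untouched.

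Most of this stands as a limit on size. A reader might infer that the SAP lays down a single chain and so carries a fixed false-claim rate of, say, 8–16% for a dose that failed remission. The documents do not support that: they give no progression rule, no endpoint correlations and no power for the secondaries.

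What does not stand is that nothing needs changing. The null actually displayed is the joint one, and the exploratory label conflicts with the alpha-controlled hierarchy instead of replacing it.

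**Conclusion.** The point holds as a gap in pre-specification with a conditional effect on error. Taken at its word, SAP 4.2.5 lets an effective dose open formal secondary testing for a dose that failed on remission, provided that two doses continue. If only one continues, the issue does not arise in the final test.

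The size depends on the unstated rule. A common chain that moves on when any dose passes gives roughly 4–18%, or about 5–15% under the mid-range assumptions, against 2.5% or less with a per-dose entry condition and chain. A joint entry condition with separate chains holds each dose to 2.5%, but the pair can reach about 5%, and a failed dose can still collect formal claims. Requiring all doses to pass controls error, but an inert dose then blocks the effective one.

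All these figures assume a full closed test for each dose and an inert dose with no effect on any endpoint. This should be fixed before unblinding; it does not threaten the primary conclusion.

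**What to change.** In SAP 4.2.5:

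1. State that a dose's ordered secondary endpoints are tested only if that dose's own primary null is rejected in the closed test.
2. State that each dose has its own chain, which stops at its first non-significant endpoint.
3. For two continuing doses, state how the one-sided 0.025 is shared across the chains. One option is 0.0125 each (0.0125 + 0.0125 = 0.025), with the full 0.025 when one dose continues. Otherwise, say plainly that control is per dose only and that the two doses together may reach about 5%.
4. Reconcile this with SAP 4.2.1, which names formal testing for the primary only, and with SAP 4.6.2, which calls the continuous secondaries exploratory. Either they belong to the hierarchy or they do not.

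The cost is wording only, with no change to data collection or sample size. A dose that fails on remission gets descriptive secondary results only, and sharing alpha lowers secondary power when two doses continue.

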#### 4.2.6. Subpopulations

Summaries on the primary and secondary efficacy endpoints will be presented by the randomization stratum, prior treatment with TNF- $\alpha$  antagonist.

#### 4.2.7. Withdrawals, Dropouts, Loss to Follow-up

For subjects who are withdrawn by the Investigator (or designee) or who voluntarily withdraw prematurely from the study, replacement subjects will be enrolled only if deemed necessary by the sponsor. Replacement subjects will be assigned a subject number by adding 300 to the number of the subject they are replacing (e.g., Subject No. 305 replaces Subject No. 005) and will be enrolled into the same randomization arm as the subject whom they are replacing.

Analyses will utilize all available data obtained from such subjects (withdrawn and replacement subjects), in accordance with the study population definitions.

